#### **4.2.7.2 Supportive Analyses**

##### **4.2.7.2.1 Responder analysis for SNOT-22 at Week 52**

An MCID of 8.90 has been established for SNOT-22 total score (Hopkins et al., 2009).

A participant who has a change from baseline  $\leq -8.9$  at Week 52 in the absence of SCS for NP, biologic for NP, or NP surgery at or prior to that time point will be defined as a

responder, otherwise the participant will be defined as a non-responder. The number and proportion of responders at Week 52 will be summarised descriptively.

For the treatment comparison, the imputed datasets as described in Section 4.2.6.1 Step 1 to Step 4 will be used. A subject will be assigned to responder or non-responder after dichotomizing the imputed values in each imputed dataset. The proportion of responders in each imputed dataset will be analysed using the logistic regression model with treatment group, baseline co-morbid asthma/AERD/NSAID-ERD status, prior NP surgery status and region (based on eCRF) as factor and baseline value as a covariate. The response variable in the model will be the binary responder status at Week 52. The analysis results from the imputed datasets will be combined using PROC MIANALYZE. Odds ratios, corresponding 95% CIs, and nominal p-value will be presented.

In addition, the same model as described above will be used in g-computation method to estimate the unconditional treatment effect. The variance will be estimated using the method proposed in [Ye et al., 2023](#) and Bannick et al., 2024 for covariate adjusted randomisation. The analysis results from the imputed datasets will be combined using PROC MIANALYZE. Unconditional difference in response rates and corresponding 95% CIs will be presented.

The same methods will be applied to each timepoint through Week 52.

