#### 4.2.6 Co-Primary Endpoints

##### 4.2.6.1 Primary Estimand Analysis

For the primary estimand the primary analysis of the co-primary efficacy endpoints (mean change from baseline in NPS at 52 weeks and mean change from baseline in NCS at 52 weeks) uses a composite variable strategy in which data collected after nasal polyp surgery will be replaced with the worst possible score (WPS). Data collected after SCS for NP will be replaced with the worst post-baseline observation prior to the SCS for NP (WOCF). Data collected after treatment discontinuation without surgery or SCS for NP will be included in the analysis. For participants whose post-baseline data are all missing, the baseline value will be used in the place of WOCF. For participants who discontinue the study without NP surgery or SCS/biologic for NP, a multiple imputation (MI) approach will be used to impute missing Week 52 value assuming missing at random (MAR). A random seed of 539612 will be used for both monotone and non-monotone imputations.

Of note, biologics are prohibited medications per the CSP Section 6.4. However, if biologics are used for NP, the same strategy used for the SCS for NP will be applied.

The following steps will be taken to generate completed datasets up to Week 52 for analysis:

**Step 1:** Data collected after date of surgery, SCS for NP, or biologic for NP treatment will be set to missing for the purpose of imputation. For the NCS, if the intercurrent event occurred prior to the last day of a bi-weekly interval, the bi-weekly mean NCS for that period and all periods afterwards will be set to missing.

**Step 2:** Based on the dataset from Step 1, the intermittent missing data will be imputed using the MCMC method in SAS PROC MI with an IMPUTE=MONOTONE statement for each treatment group separately. The imputation model will include baseline co-morbid asthma/AERD/NSAID-ERD status, prior surgery status, region, baseline value, and data at each timepoint. 100 imputed datasets will be generated.

**Step 3:** The remaining monotone missing data will be imputed using the MI procedure with the ‘MONOTONE REG’ option for each treatment group separately. The imputation model will include baseline co-morbid asthma/AERD/NSAID-ERD status, prior surgery status, region, baseline value, and data at each timepoint.

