**Step 4:** In the datasets from Step 3, replace post-surgery score with WPS, and replace post-SCS/biologic for NP score with WOCF. If a participant received both NP surgery and SCS for NP/biologic for NP, scores post-surgery will be set to WPS.

Each of the imputed datasets at Week 52 will be analysed using the analysis of covariance (ANCOVA) model with treatment group, baseline co-morbid asthma/AERD/NSAID-ERD status, prior surgery status, and region as factors (based on eCRF), and the baseline value as a covariate. Rubin’s rule will be applied to combine analysis results (point estimates and standard errors) from the imputed datasets using PROC MIANALYZE.

Descriptive statistics including number of participants, mean, standard error, and least squares (LS) means will be provided at Week 52. In addition, difference in LS means (using the observed marginal distribution of the sample covariates) and the corresponding 95% confidence intervals (CIs) will be provided along with the p-value. A single asterisk (\*) will be used to denote a result that is statistically significant at alpha = 0.05 and a double asterisk (\*\*) will be used to denote a result that is statistically significant at alpha = 0.01. Nominal p-values will be presented unless specified otherwise.

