#### **4.2.8.6 Change from baseline in ACQ-6 at Week 52 (co-morbid asthma/AERD/NSAID-ERD subset)**

The same methods described in Section [4.2.7.1.8](#) will be applied to ACQ-6 at Week 52. The same methods described in Section [4.2.7.2.2](#) through Week 52 will be applied.

The number and proportion of ACQ-6 response status and asthma control status as defined in Section [3.4.8](#) will be summarized descriptively. The proportion of responders will be analyses as described in [4.2.7.2.1](#).

The same methods will be applied to each timepoint through Week 52.

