#### **4.2.8.7 Proportion of participants with $\geq 1$ point reduction or $\geq 2$ points reduction in NPS at Week 52**

A participant with  $\geq 1$  point reduction or  $\geq 2$  points reduction in NPS at Week 52 in the absence of SCS for NP, biologic for NP, or NP surgery at or prior to that time point will be defined as a responder, otherwise the participant will be defined as a non-responder. The number and proportion of responders at Week 52 will be summarised descriptively. The proportion of responders will be analysed as described in 4.2.7.2.1.

The same methods will be applied to each timepoint through Week 52.

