#### **4.2.9.7 Proportion of NCS responders up to Week 52**

A participant with  $\geq 1$  point reduction in NCS at Week 52 in the absence of SCS for NP, biologic for NP, or NP surgery at or prior to that timepoint will be defined as a responder, otherwise the participant will be defined as a non-responder. The number and proportion of NCS responders will be analysed as described in 4.2.7.2.1.

The same methods will be applied to each timepoint through Week 52.

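### Read literally, the responder models for SNOT-22, NPS and NCS can count participants rescued with systemic corticosteroids as responders, although the SAP defines them as non-responders

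*SAP*

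**What the plan says.** SAP Section 4.2.7.2.1 defines a SNOT-22 responder at Week 52 as a participant with a change from baseline of -8.9 or lower "in the absence of SCS for NP, biologic for NP, or NP surgery at or prior to that time point". Everyone else is a non-responder.

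The next paragraph turns to the model: "For the treatment comparison, the imputed datasets as described in Section 4.2.6.1 Step 1 to Step 4 will be used". Status is then set as follows: "A subject will be assigned to responder or non-responder after dichotomizing the imputed values in each imputed dataset". The resulting binary variable goes into a logistic regression and a g-computation estimate of the rate difference, at Week 52 and at each earlier time point.

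Step 4 of Section 4.2.6.1 fixes what those datasets hold after rescue: "replace post-surgery score with WPS, and replace post-SCS/biologic for NP score with WOCF". WPS is the worst possible score. WOCF is set out earlier in the same section: "Data collected after SCS for NP will be replaced with the worst post-baseline observation prior to the SCS for NP (WOCF". Baseline takes the place of WOCF only when all post-baseline data are missing.

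Three other sections use the method:

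- **NPS, at least 1 or 2 points (4.2.8.7):** repeats the rescue-free definition, then "The proportion of responders will be analysed as described in 4.2.7.2.1".
- **NCS (4.2.9.7):** repeats the rescue-free definition, then "The number and proportion of NCS responders will be analysed as described in 4.2.7.2.1".
- **ACQ-6 (4.2.8.6):** "The proportion of responders will be analyses as described in" Section 4.2.7.2.1. Its responder definition in Section 3.4.8 has no rescue condition.

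**The concern.** The definition has two parts, a threshold and freedom from rescue. The assignment rule for the model applies only the threshold. Surgery is still handled correctly, because the worst possible score cannot be an improvement on baseline. An SCS or biologic user, however, keeps a pre-rescue score. If every post-baseline score before rescue was past the threshold, the worst of them is too, and the model counts that participant as a success.

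At stake are the odds ratios and response-rate differences for SNOT-22, NPS and NCS. One report could also show a participant as a non-responder in the descriptive table and as a responder in the model.

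**Working it through.** **1. The rule applied to constructed SCS-rescued participants**

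| Endpoint | Baseline | Scores before SCS | WOCF | Change | Threshold rule | SAP definition |
|---|---|---|---|---|---|---|
| SNOT-22 | 60 | 48, 42, 45, 50 | 50 | -10 | responder | non-responder |
| NPS, 1 point | 6 | 5, 4, 5 | 5 | -1 | responder | non-responder |
| NPS, 2 points | 6 | 4, 3, 4 | 4 | -2 | responder | non-responder |
| NCS | 2.6 | 1.5, 1.4, 1.6 | 1.6 | -1.0 | responder | non-responder |

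With surgery the score becomes 8 (NPS), 3 (NCS) or the scale maximum of 110 (SNOT-22, assumed). The change is then 0 or more, so the participant never passes. An SCS user with no post-baseline data takes the baseline value, has a change of 0 and does not pass.

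**2. The plan's own figures**

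The SAP gives no figure for the responder analyses. The rates used below come from SAP Section 1.3: 200 per arm, hazard ratio 0.33, placebo rate 35% for SCS and/or surgery and 11% for surgery. The power statements built on them reproduce, with power = Φ(|ln HR|·√(d/4) − z):

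- **Composite:** tezepelumab rate 1 − 0.65^0.33 = 0.1325; d = 200 × (0.35 + 0.1325) = 96.5 events; power at 2-sided 1% = 99.8% (stated: at least 95%).
- **Surgery:** tezepelumab rate 1 − 0.89^0.33 = 0.0377; d = 29.5 events; power at 2-sided 5% = 85.4% (stated: at least 80%).

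**3. Share with SCS but no surgery (s)**

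- Placebo: 0.35 − 0.11 = 0.24, up to 0.35.
- Tezepelumab: 0.1325 − 0.0377 = 0.0948, up to 0.1325.

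The lower bound subtracts a surgery rate that comes from a different source than the composite rate. The upper bound subtracts nothing.

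**4. Shift in the response-rate difference**

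Shift = s_t × q_t − s_p × q_p, where q is the probability that the worst of k pre-rescue changes still passes the threshold. The shift is zero when q_t/q_p = 0.24/0.0948 = 2.53, or 0.35/0.1325 = 2.64. Below that ratio the difference shrinks.

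The documents do not give q, so it was simulated (200,000 normal draws; NPS rounded to integers) under these assumptions:

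- SD 26.8 (SNOT-22) or 2.25 (NPS), the planning values
- correlation between visits 0.5 to 0.8
- mean pre-rescue change on placebo +10, 0 or −10 (SNOT-22), or +0.5, 0 or −0.5 (NPS)
- none, half or all of the planned effect (−17.4; −1.8) in rescued tezepelumab participants
- k of 1 to 11 (SNOT-22) or 1 to 4 (NPS)

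| Endpoint | q placebo | q tezepelumab | Shift (percentage points) |
|---|---|---|---|
| SNOT-22 | 0.012–0.518 | 0.011–0.755 | −11.3 to +0.9 |
| NPS, 1 point | 0.085–0.502 | 0.085–0.788 | −10.9 to +1.4 |
| NPS, 2 points | 0.029–0.331 | 0.029–0.639 | −7.2 to +1.5 |

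A SNOT-22 mid case (placebo mean 0, correlation 0.65, full effect, lower-bound shares) gives −2.9 points at k = 1, −0.4 at k = 3, +0.3 at k = 6 and +0.5 at k = 11. NCS was not simulated.

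**5. Effect on an odds ratio**

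Assume true rates of 30% and 60%, with 30% of SCS users passing in each arm. Placebo becomes 0.30 + 0.24 × 0.30 = 0.372 and tezepelumab 0.60 + 0.0948 × 0.30 = 0.628. The difference falls from 30.0 to 25.6 points and the odds ratio from 3.50 to 2.86.

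**The case against.** **The definition already governs.** The model paragraph uses the terms just defined, and the dichotomising sentence may only explain how a continuous imputed value becomes binary. The NPS and NCS sections restate the rescue condition before they cross-refer. This reading is reasonable, and a programmer might follow it. But the text does not require it, and the model paragraph states an assignment rule of its own. The point is therefore an ambiguity with two possible results, not proof that the analysis will be wrong.

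**WOCF might include baseline.** The estimand text (SAP 4.1.3.1) speaks only of the worst observation before SCS. If baseline counted, no rescued participant could pass. Section 4.2.6.1 is more specific: it says post-baseline, and it needs a baseline fallback only because baseline is otherwise excluded. The finding depends on that reading, which is the better one.

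**The extremes are unlikely.** This largely stands. The −11.3 needs a single pre-rescue visit, a placebo mean already past the threshold, no drug effect in the rescued and the upper-bound shares. Protocol Table 5 discourages SCS in the first 3 months, and SNOT-22 is scheduled at Weeks 4, 8 and 12. With k of at least 3 the SNOT-22 minimum is −7.9; with k of at least 2 the NPS minima are −8.7 and −5.2. The protocol also asks for assessments just before SCS. If that last SNOT-22 score is worse by half or one SD (assumed), the k ≥ 3 minimum becomes −5.9 or −3.5.

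**Only nominal p-values are affected.** True, and none of these analyses is in the testing hierarchy.

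**Conclusion.** The concern holds. The model's stated rule can contradict the SAP's own responder definition for SNOT-22, NPS and NCS, for users of SCS or a biologic for nasal polyps. Surgery cases are unaffected.

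The size cannot be fixed from the documents. It is plausibly a few points on the rate difference and larger only when unfavourable assumptions coincide. The direction is uncertain, but over most of the grid the literal rule dilutes the treatment effect. It inflates the difference only if rescued tezepelumab participants pass at least 2.5 to 2.6 times as often as rescued placebo participants.

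No confirmatory conclusion changes. The correction should still be made, because the NPS responder proportions are a secondary endpoint listed in the protocol and should follow their stated definition.

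**What to change.** Add two sentences to SAP Section 4.2.7.2.1:

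- In the SNOT-22, NPS and NCS responder analyses, every participant with NP surgery, SCS for NP or a biologic for NP by the time point is set to non-responder in each imputed dataset. Only the remaining participants are classified by applying the threshold to their observed or imputed values.
- This does not apply to the ACQ-6 responders in Section 4.2.8.6, whose definition has no rescue condition.

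The cost is these two sentences and one line of code. No estimand or confirmatory test changes. The change removes only the rescue-related mismatch: descriptive and modelled proportions can still differ, because the model imputes missing values under missing at random.

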#### **4.2.7.2.2 Change from baseline over time through Week 52**

Change from baseline in SNOT-22, loss of smell, NPSD TSS, and pre-BD FEV1 for each timepoint through Week 52 will be analysed using the same methods and imputed datasets as described in Sections 4.2.6.1 (primary estimand) and 4.2.6.2 (US FDA estimand). Descriptive statistics including number of participants, mean, standard error, and LS means will be provided for each timepoint. In addition, the difference in LS means and the corresponding 95% CI will be provided along with the p-values for each timepoint.

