9.4.2.2 Secondary Endpoint(s)

The analyses of the key secondary endpoints are described as follows:

The change from baseline in LMK, SNOT-22, loss of smell, and NPSD TSS at Week 52 will be analysed using the method as described in the primary analyses approach for the co-primary endpoints.

Time to first decision of surgery or SCS for NP during the 52-week treatment period will be analysed using a Cox proportional hazards model, adjusting for treatment, baseline co-morbid asthma/AERD/NSAID-ERD status, prior surgery status, and regions. The event of interest is the first SCS use or decision for nasal polyp surgery, whichever is earlier if both occur. Hazard ratios and corresponding 95% CIs and p-values will be presented. The proportion of participants having a surgery decision or SCS up to Week 52 will be estimated using the Kaplan-Meier method. The same method will be used to analyse the time to first surgery decision and time to first SCS separately.

Analysis of the change from baseline in FEV1 at Week 52 will use a treatment policy for all intercurrent events defined in Section 9.4.1.1. The population of interest will be the subset of participants with baseline co-morbid asthma/AERD/NSAID-ERD. The model includes baseline value of FEV1 as a covariate and treatment, prior surgery status, and regions as factors.

Details on statistical analyses for other secondary endpoints, including the tezepelumab serum

concentration and ADA for the evaluation of PK and immunogenicity, will be provided in the SAP.

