#### **4.2.7.1.8 Change from baseline in pre-BD FEV1 at Week 52 (comorbid asthma/AERD/NSAID-ERD subset)**

Observed pre-BD FEV1 data will be used in the analysis regardless of NP surgery and SCS/biologic for NP. Missing data up to Week 52 will be imputed assuming MAR. The intermittent missing data will be imputed using the MCMC method in SAS PROC MI with an IMPUTE=MONOTONE statement for each treatment group separately. The imputation model will include prior NP surgery status, region, baseline pre-BD FEV1 value, and data at each timepoint (both prior NP surgery status and region will be based on eCRF). 100 imputed datasets will be generated. The remaining monotone missing data will be imputed using the MI procedure with the 'MONOTONE REG' option for each treatment group separately. The imputation model will include baseline value, prior surgery status, region, and data at each timepoint. A random seed of 539612 will be used for both monotone and non-monotone imputations.

The same ANCOVA model described in Section 4.2.6.1 will be used at Week 52. Descriptive statistics including number of participants, mean, standard error, and LS means will be provided. In addition, the difference in LS means and the corresponding 95% CI will be provided along with the p-value.

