#### **4.2.8.5 Change from baseline in NPIF through Week 52**

The change from baseline in NPIF through Week 52 will be analysed using similar method as described in Section [4.2.6.1](#) (primary estimand). Step 1-3 will be repeated with no changes. In Step 4 post-surgery assessments will be replaced with WOCF (WPS not known). Each of the imputed datasets will be analysed using the analysis of covariance (ANCOVA) model shown in Section [4.2.6.1](#) through 52 weeks.

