#### **4.2.9.5 Change from baseline in pre-BD FEV1 and ACQ-6 overtime up to Week 52 (co-morbid asthma/AERD/NSAID-ERD subset)**

The same methods described in Section 4.2.7.2.2 for pre-BD FEV1 and Section 4.2.8.6 for ACQ-6 score will be applied through Week 76. Descriptive statistics including number of participants, mean, standard error, and LS means will be provided for each timepoint. In addition, the difference in LS means and the corresponding 95% CI will be provided for each timepoint.

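### SAP 4.2.7.2.2 and 4.2.8.6 send FEV1 and ACQ-6 change over time, Week 52 included, to composite-strategy datasets, although both have a treatment-policy analysis at Week 52

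*SAP*

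**What the plan says.** **FEV1 at Week 52.** Protocol 9.4.2.2 says the analysis "will use a treatment policy for all intercurrent events defined in Section 9.4.1.1". SAP 4.2.7.1.8 carries this out: observed pre-BD FEV1 "data will be used in the analysis regardless of NP surgery and SCS/biologic for NP", with a separate missing-at-random imputation in the asthma/AERD/NSAID-ERD subset.

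**FEV1 over time.** SAP 4.2.7.2.2 covers SNOT-22, loss of smell, NPSD TSS and pre-BD FEV1 together. At each timepoint through Week 52 they "will be analysed using the same methods and imputed datasets as described in Sections 4.2.6.1 (primary estimand") and 4.2.6.2 (US FDA estimand).

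**What those datasets contain.** Step 1 of 4.2.6.1 reads: "Data collected after date of surgery, SCS for NP, or biologic for NP treatment will be set to missing for the purpose of imputation". Step 4 then inserts the worst possible score (WPS) after surgery and the worst earlier observation (WOCF) after SCS or a biologic for polyps. Section 4.2.6.2 keeps data after SCS and inserts WPS after surgery or a biologic.

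**ACQ-6.** SAP 4.2.8.6 sends the Week 52 change to 4.2.7.1.8 and the change through Week 52 to 4.2.7.2.2. For responders it says: "The proportion of responders will be analyses as described in" 4.2.7.2.1, which uses the datasets from Steps 1 to 4 of 4.2.6.1.

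**Repeat of the routing.** SAP 4.2.9.5 cites 4.2.7.2.2 for FEV1 and 4.2.8.6 for ACQ-6, and says the methods "will be applied through Week 76". Its own heading and SAP Section 6 stop at Week 52.

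**The concern.** The over-time analyses include Week 52, so the same variable at the same visit is analysed under different strategies, and nothing in the SAP labels the switch or explains it.

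For FEV1 the composite instruction cannot be carried out as written. FEV1 is not a bounded score, and the SAP defines no worst possible value for it. The SAP met this difficulty for nasal peak inspiratory flow and adapted the rule in 4.2.8.5: "In Step 4 post-surgery assessments will be replaced with WOCF (WPS not known"). FEV1 has no matching rule, so a programmer would have to invent one.

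For both variables the composite route also changes what is estimated. A course of steroids or an operation for polyps would be scored as a poor lung-function or asthma-control result, whatever the spirometer or questionnaire showed. If tezepelumab reduces polyp rescue as the design assumes, the replacement falls mainly on placebo and tends to favour tezepelumab.

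**Working it through.** **Tracing the cross-references**

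| Analysis | SAP section | Leads to | After polyp surgery or rescue |
|---|---|---|---|
| FEV1 change, Week 52 (H06) | 4.2.7.1.8 | own imputation | observed value kept |
| FEV1 change, each timepoint through Week 52 | 4.2.7.2.2 | 4.2.6.1 and 4.2.6.2 | deleted, then WPS or WOCF (4.2.6.1); WPS after surgery or biologic (4.2.6.2) |
| ACQ-6 change, Week 52 | 4.2.8.6 | 4.2.7.1.8 | observed value kept |
| ACQ-6 change through Week 52 | 4.2.8.6 | 4.2.7.2.2, then 4.2.6.1 and 4.2.6.2 | as for FEV1 over time |

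Counting the FDA route, each variable has up to three Week 52 results for change from baseline. There is a further sign that the reference was not written with FEV1 in mind. The imputation model in 4.2.6.1 includes co-morbid asthma/AERD/NSAID-ERD status, which is constant in this subset. The imputation model in 4.2.7.1.8 leaves it out.

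**How many values could differ**

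Inputs, from protocol 9.2: 200 per arm; placebo rate at Week 52 of 35% for SCS and/or surgery decision and 11% for surgery decision; HR 0.33 for each; 50-70% of participants with co-morbid asthma.

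Tezepelumab rate = 1 − (1 − placebo rate)^HR:
- SCS and/or surgery decision: 1 − 0.65^0.33 = 13.3%
- surgery decision: 1 − 0.89^0.33 = 3.8%

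Check against the plan's own power statements, using the Schoenfeld formula, power = Φ(|ln HR|·√events/2 − z):
- SCS and/or surgery decision: 200 × 0.35 + 200 × 0.1325 = 96.5 events, giving 99.8% power at 2-sided 1% (stated: at least 95%)
- surgery decision: 200 × 0.11 + 200 × 0.0377 = 29.5 events, giving 85.4% power at 2-sided 5% (stated: at least 80%)

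Both agree with the protocol, so the rates are read correctly.

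Applied to the asthma subset of 200 to 280 participants (100 to 140 per arm), assuming the same rates hold there:

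| Route | Placebo | Tezepelumab | Both arms |
|---|---|---|---|
| 4.2.6.1 (surgery or SCS) | 35% (35 to 49) | 13.3% (13 to 19) | 24% (48 to 68) |
| 4.2.6.2 (surgery only) | 11% (11 to 15) | 3.8% (4 to 5) | 7% (15 to 21) |

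These are upper guides. The rates count decisions to operate, whereas replacement follows actual surgery. Biologic use is not in the rates; protocol Table 6 prohibits it.

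**Effect on the estimate**

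If the average gap between replaced and unreplaced values is the same in both arms, the treatment difference shifts by about (35% − 13.3%) × gap = 0.217 × gap under 4.2.6.1. Under 4.2.6.2 the shift is (11% − 3.8%) × gap = 0.072 × gap. The documents give no gap for either variable, so the shift cannot be put in litres or ACQ-6 points.

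**The case against.** **The confirmatory test is safe.** A reader might infer that the over-time table undermines H06. It does not. H06 is fully specified in SAP 4.2.7.1.8 and matches the protocol. Section 4.2.7.2.2 is supportive, the ACQ-6 p-values are nominal, and 4.2.9.5 is exploratory. Multiplicity control, sample size and the co-primary analyses do not change. This stands and limits the weight of the point.

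**ACQ-6 has no protocol-level treatment-policy estimand.** Protocol 9.4.2.2 sets treatment policy for FEV1 only, and SAP 4.1.3.3 gives secondary endpoints the co-primary strategies by default. This also stands. For ACQ-6 the defect is that 4.2.8.6 sets a treatment-policy analysis at Week 52 and then a composite one over a range that includes Week 52.

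**ACQ-6 responders.** Because SAP 3.4.8 defines a responder by the threshold alone, a reader might infer that the composite responder analysis is also wrong. The documents do not support that. For NPS and NCS, too, Section 3 gives only the threshold and the no-rescue condition appears in 4.2.8.7 and 4.2.9.7. The composite responder analysis follows the default in 4.1.3.3 and can be run, since ACQ-6 is scored 0 to 6. The amendment history records that the SNOT-22, ACQ-6 and NPS responder analyses were revised to align with Health Authority feedback.

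**A supportive analysis may use another strategy on purpose.** It may, but the SAP does not say so here. A deliberate composite FEV1 analysis would need a replacement value, and none is given.

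**A size in litres.** A reader might set the worst FEV1 at zero litres, assume a mean and multiply. Neither figure is in the documents, and the SAP's own precedent where WPS is unknown is WOCF.

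**Conclusion.** The point holds as an internal inconsistency in the SAP. For FEV1 over time, 4.2.7.2.2 contradicts protocol 9.4.2.2 and SAP 4.2.7.1.8 and relies on a worst possible score that does not exist. For ACQ-6 change from baseline, 4.2.8.6 sets two strategies for the same visit. Read literally, the plan gives a Week 52 result that either cannot be produced or differs in definition from the one beside it.

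At the planning rates, values could be replaced in up to about 35% of placebo and 13% of tezepelumab participants under the 4.2.6.1 route, and up to about 11% and 4% under the FDA route. This assumes that the whole-population rates apply in the asthma subset and that every surgery decision leads to an operation before Week 52. The effect on the estimate itself cannot be sized from the documents.

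The Week 76 wording in 4.2.9.5 is a separate editorial mismatch, to be corrected in the same edit. It says nothing about the estimand.

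**What to change.** - **SAP 4.2.7.2.2:** remove pre-BD FEV1 from the list and state that FEV1 over time uses the treatment-policy imputed datasets of 4.2.7.1.8 at every timepoint, with no WPS or WOCF replacement.
- **SAP 4.2.8.6:** have ACQ-6 change from baseline through Week 52 follow the same 4.2.7.1.8 approach as its Week 52 analysis. Leave the ACQ-6 responder analysis as composite.
- **SAP 4.2.9.5:** cite the corrected sections and change Week 76 to Week 52, to match its heading and Section 6.

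If a composite version of FEV1 or ACQ-6 change is wanted, label it supplementary and define the replacement values.

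The cost is a few lines of SAP wording. The imputation in 4.2.7.1.8 already covers data up to Week 52 using each timepoint, so no new data or design change is needed. The edit belongs before primary database lock, since SAP 2.1.4 rules out later updates. After that, the clinical study report should state which strategy each table uses.
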